10.1. PD Sampling schedule

PD analysis includes following PD parameters

Coagulation assays:

Prothrombin Time

aPTT

Thrombogenicity markers

Fibrinogen

D-dimer

F1+2

TAT

Sample for coagulation assays are collected at Screening and at end of study (EOS). Thrombogenicity markers are assessed pre-dose on days 2, 3, 7, 14, 21 and 28.

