8.1.2.3 Day 1 at SC dose administration (35 minutes post-IV dose)

Blood will be collected at 35-minutes post-IV dose for the following evaluations:

- Thrombogenicity markers: Fibrinogen, D-dimer, F1+2, and TAT
- PK: FIX activity

Other evaluations will include:

- Concomitant medications
- Vital signs
- Physical examination
- Clinical signs of thrombosis (see [Appendix A](#))
- Review of diary entry of investigational drug administration, injection site assessment, adverse events, bleeding episodes & treatment
- Adverse events

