8.1.3.1 Washout period evaluations (Day 29, 30, 31, 32, and 33)

- Concomitant medications
- Clinical signs of thrombosis (see **Appendix A**)
- Thrombogenicity markers: Fibrinogen, D-dimer, F1+2, and TAT
- PK: FIX activity
 - Daily FIX activity levels will be measured, unless FIX activity level is known to be < 5% as measured by local laboratory
- Review of diary entry of investigational drug administration, injection site assessment, adverse events, bleeding episodes & treatment
- Adverse events

Dalcinonacog alfa_DLZ-201 VERSION 2.0, Amendment 1

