3.3. Brief Description

This is a single-center, open-label Phase 2b study designed to evaluate the PK, PD, efficacy and safety of SC prophylaxis treatment regimens with CB2679d in adult subjects with hemophilia B. It is an open-label study, so subjects and members of the clinical study team will not be blinded to treatment. It is estimated that it will take approximately 6 months from subject enrollment until completion of last subject last visit. The study will enroll and dose SC a total of 6 adult male subjects with severe congenital hemophilia B. Participants will be given a SC prophylaxis CB2679d regimen over a 4-week period, with the goal to achieve steady-state levels above 12% FIX activity when dosed daily.

Each subject will participate for approximately 4-weeks (28 days) of SC CB2679d drug administrations:

Treatment: Day 1 to Day 28: Each participant will receive an intravenous (IV) loading dose of 50 IU/kg followed 35 ± 5 minutes later by a SC dose of 100 IU/kg. Daily SC doses of 100 IU/kg will be administered until Day 28 (28 total SC doses). On Day 1, PK, PD, and safety assessments will be done at pre- IV dose and repeated 35 (± 5) minutes later prior to the SC dose. Subsequent PK, PD and safety assessments will be performed pre-dose on days 2, 3, 7, 14, 21 and 28.

Washout Period: PK, PD, and safety assessments will be done on Days 29, 30, 31, 32 and 33. Daily FIX activity levels will be measured, unless FIX activity level is known to be < 5% as measured by local laboratory.

An End of Study visit will occur 30 days (± 2 days) after the last dose of study drug.

This document is confidential.

Statistical Analysis Plan for Interventional Studies
Sponsor: Catalyst Biosciences, Inc.; Protocol No.: DLZ-201

Subjects will sign an informed consent form (ICF) at the Screening Visit, prior to any study procedures. Eligibility to participate in the study will be determined by inclusion and exclusion criteria from medical history, hemophilia history, laboratory investigations, and electrocardiogram (ECG). The screening period duration may be up to 4 weeks.

At enrollment, subjects will receive training on diary entry of self-administered study drug administration, injection site assessment, bleeding episodes and treatment, and evaluation and entry of adverse events (AEs).

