3.8. Study Procedures and Flowchart

[figure not shown]

Figure 1: Schematic of study design

This document is confidential.

Statistical Analysis Plan for Interventional Studies
Sponsor: Catalyst Biosciences, Inc.; Protocol No.: DLZ-201

Study Period	Screening	Treatment Period								Wash-out ⁸	Unscheduled Visit	End of Study ⁹
Study Day	Day -28 to -1	Day 1, IV Pre-dose (-5 min)	Day 1, SC dose, 35 (± 5) min Post IV	Day 2	Day 3	Day 7 (± 1 day)	Day 14 (± 1 day)	Day 21 (± 1 day)	Day 28 (± 1 day)	Days 29, 30, 31, 32, 33		
Informed Consent	X											
Demographic Parameters	X											
Inclusion and Exclusion Criteria	X											
Medical and Hemophilia History ²	X										X	
Vital Signs	X	X	X	X	X	X	X	X	X		X	X
Height (screening only) & Weight	X	X									X	X
Physical Examination ²	X	X	X	X	X	X	X	X	X		X	X
Clinical Signs of Thrombosis ³	X	X	X	X	X	X	X	X	X		X	X
Hematology and Chemistry ⁴	X	X		X		X	X	X	X		X	X
Coagulation Assays ⁵	X											X
Thrombogenicity Markers ⁶	X	X	X	X	X	X	X	X	X		X	X
Pharmacokinetic Sampling ⁶	X	X	X	X	X	X	X	X	X		X	X
Immunogenicity Assays ⁶	X					X	X	X	X		X	X
Genotyping	X											
ECG	X											
Diary entry training ⁶		X										
Diary entry of any bleeding episodes, AEs, injection site reactions ⁶												→
Adverse Events												→
Concomitant Medications	X											→
CB2679d ⁷ Administration ⁸			X									

- As per Standard of Care at hemophilia treatment center.
- Complete evaluation at Screening followed by interim targeted evaluation, per Investigator's discretion, as indicated on presentation of subject at study visit. Joint evaluation will be performed at Screening.
- Clinical Signs of Thrombosis per protocol
- Local Laboratory: Hematology – complete blood count (CBC) and platelet count. Chemistry - Sodium, potassium, chloride, bicarbonate, hepatic enzymes (ALT, AST, Gamma-glutamyl transpeptidase (GGT)), bilirubin, albumin, creatinine. For Days 2, 3, 7, 14, 21, and 28, blood will be collected at Pre-dose (- 5 minutes).
- Central Laboratory: Coagulation assays – Prothrombin time and aPTT. Thrombogenicity markers – Fibrinogen, D-dimer, F1+2, and TAT. Pharmacokinetics – FIX activity. Immunogenicity assays – to CB2679d and BeneFIX[®]. For Days 2, 3, 7, 14, 21, and 28, blood will be collected at Pre-dose (- 5 minutes).
- Diary entry training and entry consists of investigational drug administration, injection site assessment, adverse events, any bleeding episodes & treatment.

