8.2. Secondary Efficacy Endpoints and Analyses

8.2.1. Change in FIX activity levels from pre-dose

Actual and change from baseline (including maximum absolute change from baseline) values for FIX activity level will be summarized by time point for the PK and the Safety Population. Different PK parameters will be summarized as well as described in [Section 9](#).

8.2.2. Occurrence of clinically significant levels of thrombogenicity markers resulting from SC administration of CB2679d

The following thrombogenicity markers during the treatment period will be assessed for the PD and the Safety Population:

- Fibrinogen,
- D-dimer,
- F1+2,
- TAT

Detailed PD analysis is described in [Section 10](#).

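### SAP 10.1 gives the thrombogenicity markers a six-day pre-dose schedule that conflicts with the protocol and the rest of the SAP, and SAP 8.2.2 and 6.2.1 confine them to the treatment period, leaving washout outside the endpoint and the maximum change

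*SAP*

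**What the plan says.** SAP 10.1 (PD sampling schedule) reads: "Thrombogenicity markers are assessed pre-dose on days 2, 3, 7, 14, 21 and 28". The sentence before it places the coagulation assays at Screening and end of study, which is their complete schedule in the protocol.

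Protocol V2.0 asks for more marker samples. Section 8.1.2.3 says "Blood will be collected at 35-minutes post-IV dose for the following evaluations" and puts the four markers first in the list that follows. Section 8.1.3.1, for Days 29 to 33, lists "Thrombogenicity markers: Fibrinogen, D-dimer, F1+2, and TAT", and the same item stands under Screening (8.1.1), Day 1 pre-dose (8.1.2.1) and end of study (8.1.3.3). The schedule of activities in protocol 1.3 agrees.

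The SAP is not consistent with its own 10.1. Section 3.3 says of Day 1: "PK, PD, and safety assessments will be done at pre- IV dose and repeated 35 (± 5) minutes later prior to the SC dose". It says of washout: "PK, PD, and safety assessments will be done on Days 29, 30, 31, 32 and 33". In Table 1 the row "Thrombogenicity Markers" is marked at Day 1 pre-IV, Day 1 post-IV and end of study. Section 6.4 says data are analysed by the protocol's scheduled visits, and its window table has a Day 1 post-IV row but none for washout or end of study.

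On the endpoint, SAP 8.2.2 says: "The following thrombogenicity markers during the treatment period will be assessed for the PD and the Safety Population". Section 6.2.1 takes the maximum change from baseline over treatment-period visits. The Note to File drops the word absolute from that definition and keeps the period.

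**The concern.** Marker levels are a secondary objective and a secondary endpoint, and thromboembolic events are an adverse event of special interest. Section 10.1 is where a programmer would look for the PD time points, and 10.2, which follows directly, asks for summaries by time point. The Note to File replaces the individual and mean marker profiles with box plots by visit, so the list of visits now decides what the figures show.

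Two separate things are at stake. First, a wrong schedule statement could lead to tables and plots without the post-IV, washout and end-of-study values, and it does not name the baseline. Second, the treatment-period wording in 8.2.2 and 6.2.1 puts washout values outside the endpoint and the maximum even if 10.1 is corrected. SAP Section 13, which declares departures from the protocol, mentions no reduced marker schedule, and the Note to File shows no change to 10.1.

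**Working it through.** The plan gives no figure to reproduce here. The check is a count of scheduled marker samples per subject, taken from protocol V2.0 Sections 1.3 and 8.1.

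| Time point | Protocol V2.0 | Samples | In SAP 10.1 | In treatment period |
|---|---|---|---|---|
| Screening | 8.1.1 | 1 | no | before dosing |
| Day 1 pre-IV (baseline) | 8.1.2.1 | 1 | no | baseline |
| Day 1, 35 min post-IV | 8.1.2.3 | 1 | no | yes |
| Days 2, 3 pre-dose | 8.1.2.4 | 2 | yes | yes |
| Days 7, 14, 21, 28 pre-dose | 8.1.2.5 | 4 | yes | yes |
| Days 29 to 33 | 8.1.3.1 | 5 | no | no |
| End of study | 8.1.3.3 | 1 | no | no |

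Treatment period is read as Day 1 to Day 28. Both schedules head those columns that way and give washout its own column, and SAP 9.1 separates the two periods in the same manner. Appendix B of protocol V2.0 still shows an Hour 7 draw on Day 1 and no Day 3 visit. Sections 1.3 and 8.1 agree with each other on the markers, so the count follows them.

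1. All scheduled samples: 1 + 1 + 1 + 2 + 4 + 5 + 1 = 15 per subject.
2. Post-baseline: 15 − 2 = 13.
3. Named in SAP 10.1: 2 + 4 = 6, which is 6/13 = 46% of post-baseline and 6/15 = 40% of all. Post-baseline samples not named: 1 post-IV + 5 washout + 1 end of study = 7.
4. Inside the treatment period: 1 + 6 = 7 of 13. Outside: 5 + 1 = 6 of 13. For six subjects, 6 × 6 = 36 scheduled samples fall outside the endpoint and the maximum.
5. Baseline: SAP 6.2.1 defines it as the last assessment before first study drug, which is the Day 1 pre-IV sample when available. Section 10.2 needs it and 10.1 does not list it.

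Do the washout samples still reflect exposure? Protocol 2.2.2 gives a half-life of 63.2 hours (interquartile range 60.2 to 64.0) after daily SC dosing. Assuming simple exponential decline from the last dose, the fraction remaining is 2^(−t/63.2):

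- Day 29, t about 24 h: 2^(−24/63.2) = 0.77 (0.76 to 0.77 over the interquartile range).
- Day 33, t about 120 h: 2^(−120/63.2) = 0.27 (0.25 to 0.27).

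Day 29 sits at the same point after a dose as the earlier pre-dose samples. The Day 28 draw precedes the 28th SC dose, so Day 29 is also the first marker sample after the full course.

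**The case against.** The strongest reply is that 10.1 is descriptive. It does not say that only those days are used, and it cannot be exhaustive because it leaves out the baseline that 10.2 requires. Section 6.4 sends the analyst to the protocol's visits, Sections 3.3 and Table 1 carry most of the missing samples, 10.2 and 10.3 work by time point without restricting days, and Listing 16.2.6.3 should hold every value. The washout cell for the markers in Table 1 appears blank as extracted, but so does the PK cell, although SAP 9.1 schedules washout PK, so the blank shows no intent. Clinical thrombotic events are reported separately under 11.3 and 11.9.

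Most of this stands. A reader might infer from 10.1 that the tables omit half the marker data. The documents do not establish that, only that two readings are open. The reply also shows that 8.2.2 by itself keeps the Day 1 post-IV sample, which lies within the treatment period. That sample precedes all SC dosing, so it cannot show an SC effect, which is what the endpoint is about.

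What the reply does not meet is the treatment-period limit. Section 6.4 has no washout or end-of-study row, and neither 6.4 nor the other sections widen 8.2.2 or 6.2.1.

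**Conclusion.** The point holds in two parts. SAP 10.1 misstates the marker schedule: it names 6 of 13 post-baseline time points, omits the baseline, and conflicts with the protocol and with SAP 3.3, 6.4 and Table 1. SAP 8.2.2 and 6.2.1 then leave 6 of 13 outside the endpoint and the maximum, five of them washout samples taken while, on the plan's own half-life, roughly 77% down to 27% of the level remains. The second part rests on reading treatment period as Days 1 to 28; the percentages also rest on simple exponential decline. In a descriptive study of six subjects, with values listed individually, this is worth correcting but does not threaten the trial.

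Two further readings are tempting and should not be relied on:

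- That the 35-minute sample has the highest FIX activity. No IV recovery or post-IV level is given. With an assumed recovery of 0.5 to 1.3 IU/dL per IU/kg, the load gives 50 × 0.5 = 25% to 50 × 1.3 = 65%. Scaling the SC-only median of 15.7% at 150 IU/kg to steady state at 100 IU/kg gives about 13% (15.7 / 0.794 × 100/150 = 13.2), which would make the post-IV level look several times the trough. But that trough ignores the IV load, and the prior cohort given IV plus SC dosing rose above 30%. The post-IV value exceeds 30% only if recovery is above 30/50 = 0.6. It is simply the only marker sample scheduled shortly after the IV load.
- That washout sampling covers the 24 hours after the final dose. The Day 28 draw is pre-dose and the next is Day 29, so no marker sample is scheduled within that interval.

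**What to change.** - **SAP 10.1:** replace the sentence with the protocol schedule: Screening; Day 1 pre-IV, named as baseline; Day 1 at 35 minutes post-IV; pre-dose on Days 2, 3, 7, 14, 21 and 28; Days 29 to 33; end of study.
- **SAP 6.4:** add washout and end-of-study rows to the window table.
- **SAP 8.2.2, and 6.2.1 for these markers:** run the window from first dose through washout and end of study, and carry the same wording into the text revised by the Note to File.
- **Presentation:** show the Day 1 post-IV, pre-SC sample on its own line as reflecting the IV load, so that it is not counted as an effect of SC administration.

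The cost is SAP wording and small changes to the table and box-plot programs. No visit, sample or assay is added, because the protocol already schedules every draw.

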10.2. PD Biomarkers Analysis

Actual and change from baseline (including maximum absolute change from baseline) for all PD parameters (e.g., Prothrombin Time, aPTT, Fibrinogen, D-dimer, F1+2, and TAT) will be summarized by time point. Coagulation assays and thrombogenicity markers will be tabulated separately.

10.3. Presentation of PD Data

Actual measurements for each parameter will be listed by subject and time point. The actual assessment time or sampling of PD parameters will be listed for each subject and will include the deviation only if the sample was taken after the dose instead of pre-dose, if applicable.

Subjects with protocol deviation affecting PD may be flagged and excluded from PD Population.

Individual PD data-time profiles of thrombogenicity markers for actual measurement and change from baseline results will be presented with all subjects in the same figure on linear scales.

Mean +/- SD PD data-time profiles of thrombogenicity markers for actual measurements and change from baseline results will be presented in the same figure.

This document is confidential.

Statistical Analysis Plan for Interventional Studies
Sponsor: Catalyst Biosciences, Inc.; Protocol No.: DLZ-201

11. Safety

The population used for safety analyses will be the Safety Population. No inferential statistics will be performed; only summary statistics will be provided. Missing safety data will not be imputed. Safety will be assessed on the basis of AE, hematology and chemistry, ECG, physical examinations, vital signs, occurrence of a confirmed antibody response to CB2679d, occurrence of thrombotic events, and whether it is inhibitory and cross-reactive to BeneFIX and difficulties due to hemophilia after last dose of study drug.

11.1. Extent of Exposure

Exposure to study drug (in days) will be calculated:

Exposure overall = number of days where study drug was administered.

Exposure will be summarized and listed. Details on study drug administration and drug accountability will be listed as well.

11.2. Treatment Compliance

Study drug compliance (%) is calculated as ratio of the number of days study drug reported as administered and the number of days of administration expected. [in days]. Compliance will be summarized and listed.

11.3. Adverse Events

Adverse events will be coded using MedDRA Version 20.1 to classify events under primary SOC and PT. A treatment emergent adverse event (TEAE) is defined as an AE that either begins after the first dose of study drug in this study or worsens after the first dose of study drug in this study but not later than the date of last dose + 30 days. AEs with a missing start date and a stop date on or after the first dose of study medication, or AEs with both a missing start and stop date are also defined as TEAE.

Number of subjects per TEAE and number of events per TEAE below will be summarized by SOC and PT. Multiple occurrences of an AE are counted only once per subject per SOC and PT for summary tables:

- Incidence of all TEAEs
- Incidence of all TEAEs by maximum severity (in the following order: severe, moderate and mild). Missing severity will be considered as not recorded.
- Incidence of TEAE by relationship to study drug (related, not related). Missing relationship will be considered as related.
- Incidence of serious TEAEs
- Incidence of serious TEAEs by relationship to study drug
- Incidence of TEAEs leading to study drug discontinuation
- Incidence of Injection Site Reactions
- Incidence of Adverse Events of Special Interest (AESI)

Definition of AESI is documented in Section 8.4.7 of the Protocol.

All AEs will be listed.

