9. End of Study Visit will occur 30 ± 2 days after the last dose.

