4. STUDY DESIGN

4.1 OVERALL DESIGN

This is a single-center, open-label Phase 2b study designed to evaluate the PK, PD, efficacy and safety of SC prophylaxis treatment regimens with CB2679d in adult subjects with hemophilia B. It is an open-label study, so subjects and members of the clinical study team will not be blinded to treatment. It is estimated that it will take approximately 6 months from when the study opens enrollment until completion of last patient last visit. The study will enroll a total of 6 adult male subjects with severe congenital hemophilia B. Participants will be given SC prophylaxis CB2679d regimens over a 4-week period, with the goal to achieve steady-state levels above 12% FIX activity when dosed daily.

Each subject will participate for approximately 4-weeks (28 days) of SC CB2679d drug administrations:

Treatment: Day 1 to Day 28: Each participant will receive an IV loading dose of 50 IU/kg followed 35 ± 5 minutes later by a SC dose of 100 IU/kg. **Daily** SC doses of 100 IU/kg will be administered until Day 28 (28 total SC doses). On day 1, PK, PD, and safety assessments will be done at pre-IV dose and repeated 35 (± 5) minutes later prior to the SC dose. Subsequent PK, PD and safety assessments will be performed pre-dose on days 2, 3, 7, 14, 21 and 28.

Washout Period

PK, PD, and safety assessments will be done on Days 29, 30, 31, 32 and 33. Daily FIX activity levels will be measured, unless FIX activity level is known to be < 5% as measured by local laboratory.

An End of Study visit will occur 30 days (± 2 days) after the last dose of study drug.

Subjects will sign an ICF at the Screening Visit, prior to any study procedures. Eligibility to participate in the study will be determined by inclusion and exclusion criteria from medical history, hemophilia history, laboratory investigations and ECG. The screening period duration may be up to 4 weeks.

At enrollment, subjects will receive training and diary entry of self-administered investigational drug administration & injection site assessment, bleeding episodes & treatment, evaluation & entry of AEs.

Treatment of a spontaneous or traumatic bleeding episode: Subjects will use their current prescribed treatment regimen for any spontaneous or traumatic bleed that occurs while on study drug. If treatment for a spontaneous or traumatic bleeding episode is needed, then subjects will contact the clinical

Dalcinonacog alfa_DLZ-201 VERSION 2.0, Amendment 1

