8.4.5 Adverse Event Reporting

Members of the study team will record all reportable events with start dates occurring any time after informed consent is obtained until study completion, or discharge, for non-serious AEs. At each study visit, the investigator will inquire about the occurrence of AE since the last visit. Events will be followed for outcome information until resolution or stabilization.

The Investigator will categorize the **outcome** of each AE according to the definitions below:

Resolved: The subject recovered from the AE.

Ongoing: At the time of the last assessment, the event is ongoing, with an undetermined outcome. Note: Ongoing AEs are not considered resolved as a result of death. No AE stop date should be recorded with an AE that is ongoing.

Dalcinonacog alfa_DLZ-201 VERSION 2.0, Amendment 1

Chronic/Stable: At the time of the last assessment, the event is ongoing and stabilized, with no change to the event outcome anticipated.

Unknown: There is an inability to access the subject or the subject's records to determine the outcome (ie, subject withdraws consent or is lost to follow-up).

All protocol-defined adverse events will be reported from the time a patient is enrolled in the study until the end of study visit.

Spontaneous or traumatic bleeding events will not be reported as an AE unless considered serious and should then be reported per the standard process for reporting.

All bleeds should be entered into the diary including spontaneous bleeds, traumatic bleeds or bleeds related to procedure/surgery (see **Section 4.1**). Only bleeds (spontaneous bleeds, traumatic bleeds or bleeds related to procedure/surgery) that are considered serious as per definition (see **Section 8.4.6**) should be reported as an SAE in the CRF. Non-serious bleeds are not considered adverse events for the purpose of this protocol and should not be reported as adverse event in the eCRF.

The study drug has the potential risk of causing the following AEs based on information associated with other drugs in the same category, ie, FIX agents for treatment of hemophilia; these are:

Thrombotic events (see [Appendix A](#))

Based on information associated with other drugs for treatment of hemophilia, the study drug has the potential risk of causing thrombotic events. See [Appendix A](#) for signs and symptoms listed for the subjects and the study team personnel as those requiring urgent reporting and attention.

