8.4.6 Serious Adverse Event Reporting

Members of the study team will record all reportable events within 24 hours of knowledge of the SAE with start dates occurring any time after informed consent is obtained until 30 days after the last day of study participation. At each study visit, the investigator will inquire about the occurrence of SAEs since the last visit. Events will be followed for outcome information until resolution or stabilization.

The Investigator will categorize the **outcome** of each SAE according to the definitions below:

Resolved: The subject recovered from the AE.

Ongoing: At the time of the last assessment, the event is ongoing, with an undetermined outcome. Note: Ongoing AEs are not considered resolved as a result of death. No AE stop date should be recorded with an AE that is ongoing.

Chronic/Stable: At the time of the last assessment, the event is ongoing and stabilized, with no change to the event outcome anticipated.

Death: The AE directly caused death.

Unknown: There is an inability to access the subject or the subject's records to determine the outcome (ie, subject withdraws consent or is lost to follow-up).

Definitions:

Death: Any event resulting in a subject's death must be reported as an SAE. However, death, in and of itself, is not an AE; it is only an outcome. The cause of death is the AE. Therefore, the investigator should make every effort to obtain and document the cause of death for all subjects who die during the study. If, despite all efforts, the cause of death remains unknown, the AE should be documented as an "unspecified fatal event".

Life threatening AE: Any AE that places the patient or subject, in the view of the investigator, at immediate risk of death from the reaction as it occurred (ie, it does not include a reaction that, had it occurred in a more severe form, might have caused death).

Hospitalization: It should be noted that hospitalization, in and of itself, does not represent an SAE. It is the AE leading to the subject's hospitalization that becomes "serious" when it requires inpatient care. Consequently, an SAE should not be reported in the case of pre-planned hospitalizations for pre-existing conditions that did not worsen during the study.

Dalcinonacog alfa_DLZ-201 VERSION 2.0, Amendment 1

Disability: A substantial disruption of a person's ability to conduct normal life functions.

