3.7. Administration of Study Drug

Each subject will receive a CB2679d loading dose of 50 IU/kg IV, followed 35 ± 5 minutes later with a SC dose of 100 IU/kg, and SC administration daily until Day 28 (total 1 IV dose and 28 SC doses).

This document is confidential.

Statistical Analysis Plan for Interventional Studies
Sponsor: Catalyst Biosciences, Inc.; Protocol No.: DLZ-201

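### The TEAE window closes at last dose + 30 days, but AEs are collected to an end-of-study visit allowed up to + 32, so events dated + 31 or + 32 miss the TEAE tables

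*SAP*

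**What the plan says.** SAP 11.3 defines a TEAE as "an AE that either begins after the first dose of study drug in this study or worsens after the first dose of study drug", and adds the limit "but not later than the date of last dose + 30 days". Undated events are kept: "AEs with both a missing start and stop date are also defined as TEAE". The TEAE summaries that follow include serious events and adverse events of special interest (AESIs), and all AEs are to be listed.

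The current protocol (Version 2.0) sets a longer collection period. Section 4.1 states "An End of Study visit will occur 30 days (± 2 days) after the last dose of study drug". Section 4.2, the footnotes to the Schedule of Activities in 1.3, and SAP 3.3 give the same window. Section 8.4.5 states "All protocol-defined adverse events will be reported from the time a patient is enrolled in the study until the end of study visit". Section 8.4.6 has serious events recorded "until 30 days after the last day of study participation".

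The EOS visit also carries an immunogenicity sample, the only scheduled one after Day 28 (SAP 11.8). Protocol 8.4.7 makes antibody formation an AESI. The available rows of the July 2020 Note to File pass from SAP 10.3 to 11.4 and do not revise 11.3.

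**The concern.** The analysis window and the collection window should close together, or the plan should say why they do not. Here the analysis window can close one or two days before collection of non-serious events ends. Whether an event dated at the visit counts as treatment-emergent can then depend on when the clinic booked the visit rather than on anything about the event.

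The visit concerned is not a routine one. A subject who seroconverts after the Day 28 sample can be detected only there, apart from unscheduled draws. Protocol 2.2.2 reports neutralizing antibodies in both subjects of cohort 6 in the preceding study, so an antibody AESI at this visit is foreseeable. If its onset were dated by an EOS sample taken on + 31 or + 32, the definition would exclude it.

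Serious events have a longer gap of the same kind. They are collected for about another month after the window closes, but the two serious-event tables in the SAP index (14.3.1.5 and 14.3.1.6) are both limited to treatment-emergent events.

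**Working it through.** The plan gives no figure on this point to reproduce. The check is calendar arithmetic, with all offsets counted from the last dose.

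**Inputs**
- TEAE limit: + 30 (SAP 11.3).
- EOS visit: 30 ± 2, that is + 28 to + 32 ("End of Study Visit will occur 30 ± 2 days after the last dose", Protocol 1.3).
- AE collection: to the EOS visit (Protocol 8.4.5).
- SAE collection: last day of participation + 30 (Protocol 8.4.6).
- Planned last dose: Day 28 ("SC administration daily until Day 28 (total 1 IV dose and 28 SC doses", SAP 3.7).
- Subjects: 6 (SAP 3.5).

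**Step 1, visit against window.** The window closes on study Day 28 + 30 = 58. EOS may fall on Day 28 + 28 = 56 to Day 28 + 32 = 60. Days 59 and 60 (+ 31 and + 32) lie outside, which is 2 of 5 permitted days. If interruptions move the last dose, the offsets do not change.

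**Step 2, which events are affected.** Classification follows when an event begins or worsens, not when it is found.

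| Event | Collected? | TEAE? |
|---|---|---|
| Reported at a + 32 visit, onset by + 30 | yes | yes |
| Reported at a + 32 visit, both dates missing | yes | yes |
| Onset or worsening dated + 31 or + 32 | yes | no |

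An undated event is therefore kept, while a fully documented one at + 31 is dropped.

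**Step 3, serious events.** I take the last day of participation to be the EOS visit. Collection then ends between 28 + 30 = + 58 and 32 + 30 = + 62. Time collected beyond the TEAE limit is 58 − 30 = 28 to 62 − 30 = 32 days.

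**Step 4, scale.** One subject in six is 1/6 = 16.7 percentage points of incidence, as for any single event in a trial of this size. The documents give no distribution of EOS dates. As an illustration, let p be the chance that a visit falls on + 31 or + 32, independently between subjects. The chance that at least one of six visits does so is 1 − (1 − p)^6:
- p = 0.10: 1 − 0.90^6 = 0.47
- p = 0.20: 1 − 0.80^6 = 0.74
- p = 0.40 (uniform over the five days): 1 − 0.60^6 = 0.95

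These are chances of a visit outside the window. The chance of an event dated on one of those days is smaller, and the documents give no basis for estimating it.

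**Step 5, after the change.** If the window runs through the later of + 30 and the EOS visit, 0 of 5 permitted visit days fall outside.

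**The case against.** The strongest reply is that a 30-day limit is a reasonable choice and little depends on it. It equals the nominal follow-up. With the half-lives in Protocol 2.2.2 (63.2 hours after repeated dosing, 66 to 103 hours after single doses), 30 days is 720 hours, or 720/103 = 7.0 to 720/63.2 = 11.4 half-lives. Collecting serious events for longer than the TEAE window is not in itself an error. All of this stands. It supports 30 days as a nominal limit, but gives no reason to cut off events collected at a visit the protocol counts as on time.

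Three stronger readings are tempting, and the documents do not support them.

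- A reader might infer that whatever is first found at a late EOS visit is lost from the TEAE tables. It is not, because the definition turns on onset or worsening.
- A reader might infer that antibodies first detected at that visit go unreported. No passage dates an antibody AE to the sample; with the previous sample on Day 28, onset could be placed earlier. SAP 11.8 and Table 14.3.4.3.1 count antibody-positive subjects at each time point, EOS included, and Listing 16.2.8.6 shows the results. Exclusion from the AESI table is itself arguable: SAP 11.3 places that summary under a TEAE lead-in, but the title of Table 14.3.1.8 carries no such limit.
- A reader might infer that serious events after + 30 are not reported. They appear in Listing 16.2.7.3, deaths in Listing 16.2.7.5, and thrombotic events have their own summary under SAP 11.9 with no stated time limit.

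The sentence in SAP 11.3 can also be parsed so that the limit attaches only to worsening. New-onset events would then have no upper limit, and the gap would remain only for worsening. That weakens the point as to size, but it shows that two programmers could build different TEAE flags from the same text.

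**Conclusion.** The mismatch is real and minor. If the limit governs both onset and worsening, AEs dated + 31 or + 32 are collected under the protocol but excluded from the TEAE and serious-TEAE tables, and arguably from the AESI table. If it governs worsening only, the wording still needs settling. The loss is confined to table counts and at most two days per subject for non-serious events. For serious events, 28 to 32 days of collected data have listings but no AE table. The study has six subjects, makes no inferential safety analysis and lists every AE, so no conclusion is likely to turn on this.

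The conclusion rests on two assumptions: that the last day of participation means the EOS visit, and that no part of the Note to File outside the available rows changes SAP 11.3. An effect on an antibody AESI depends further on its onset being dated by the EOS sample, which the documents leave open.

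**What to change.** In SAP 11.3, define a TEAE as an AE with onset or worsening after the first dose and through the later of last dose + 30 days and the EOS visit, and state that the limit applies to both onset and worsening. Taking the later of the two keeps the window from shortening when the visit falls on + 28 or + 29. Report serious events with onset after the window in a separate row of the serious-event tables. It would also help to state how the onset of an antibody AE is dated.

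The cost is a few lines of SAP text and one table row, with no new data collection. The downside is that the window length then varies by up to two days between subjects (30 to 32 days after the last dose).
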